-----------------	---------------------------	-----------

LIST OF APPENDICES

Appendix 1	Schedule of Visits and Procedures	66
Appendix 2	Procedures	68
Appendix 3	Sponsor’s Obligations	76
Appendix 4	Investigator’s Obligations	77
Appendix 5	Declaration of Helsinki	80
Appendix 6	Study Monitoring	83
Appendix 7	Sample SAS Code	84

LIST OF ABBREVIATIONS AND DEFINITIONS OF TERMS

AE	Adverse Event
A/G	Albumin/globulin
ALT	Argon Laser Trabeculoplasty
ALT	Alanine aminotransferase
AST	Aspartate aminotransferase
BCVA	Best Corrected Visual Acuity
BP	Blood Pressure
BUN	Blood urea nitrogen
CFR	Code of Federal Regulations
CI	Confidence Interval
CRF	Case Report Form
CRO	Contract Research Organization
CV	Curriculum Vitae
DHHS	Department of Health and Human Services
EDC	Electronic Data Capture
ETDRS	Early Treatment of Diabetic Retinopathy Study
FDA	Food and Drug Administration
GCP	Good Clinical Practice
hCG	Human Chorionic Gonadotropin
HR	Heart Rate
ICF	Informed Consent Form
ICH	International Conference on Harmonization
IND	Investigational New Drug
IOP	Intraocular Pressure
IP	Investigational Product
IRB	Institutional Review Board
ITT	Intent-to-Treat
IWRS	Interactive Web Response System
LASIK	Laser-Assisted In Situ Keratomileusis
LDPE	Low Density Polyethylene
LOCF	Last Observation Carried Forward
logMAR	Logarithm of the Minimum Angle of Resolution
mmHg	Millimeters of Mercury
MedDRA	Medical Dictionary for Regulatory Activities

OAG	Open-Angle Glaucoma
OHT	Ocular Hypertension
OTC	Over-the-Counter
OU	Both Eyes
PM	Evening
PP	Per Protocol
PRK	Photorefractive Keratectomy
PT	Preferred Term
QD	Once Daily
ROCK	Rho Kinase
Rx	Medical Prescription
SAE	Serious Adverse Event
SAR	Suspected Adverse Reaction
SAS	Statistical Analysis Software
SD	Standard Deviation
SITA	Swedish Interactive Thresholding Algorithm
SLT	Selective Laser Trabeculoplasty
SOC	System Organ Class
SOP	Standard Operating Procedure
SSAR	Serious Suspected Adverse Reaction
SUSAR	Serious Unexpected Suspected Adverse Reaction
UA	Urinalysis
US	United States

1. INTRODUCTION

1.1 Investigational Product

Glaucoma is a progressive optic neuropathy that causes characteristic loss of visual fields and can eventually lead to blindness. A major risk factor for glaucomatous visual field loss is elevated intraocular pressure ([AGIS 2000](#)).

The need for improved efficacy of glaucoma medications is supported by several clinical studies. Studies such as the Early Manifest Glaucoma Trial ([Heijl 2002](#)), the Ocular Hypertension Treatment Study ([Kass 2002](#); [Kass 2010](#)), and the Collaborative Normal Tension Glaucoma Study Group ([Collaborative Normal-Tension Glaucoma Study Group 1998](#)) support the general conclusion that every millimeter of reduction in intraocular pressure (IOP) is significant for delaying disease progression. This conclusion holds true not only for high risk ocular hypertensive and glaucoma subjects with elevated IOPs but also for glaucoma subjects with IOPs in the normal range. Thus, the goal for treating subjects should be to lower IOP to the point that it prevents further damage to the optic nerve and achieve this without sacrificing safety or convenience.

Inhibitors of Rho kinase (ROCK) have emerged as a new class of IOP-lowering agents and are currently being tested in the clinic ([Chen 2011](#); [Kopczynski 2014](#)). Netarsudil mesylate (AR-13324) is a novel Rho kinase and norepinephrine transporter inhibitor developed at Aerie Pharmaceuticals, Inc. for topical ophthalmic use for lowering IOP. In both rabbit and monkey studies, netarsudil produces large reductions in IOP with a longer duration of action than reported for previously characterized Rho kinase inhibitors. Netarsudil ophthalmic solution has been shown to provide significant IOP lowering when dosed once-daily (QD) in the evening (Clinical Study Reports [AR-13324-CS202](#), [AR-13324-CS301](#), [AR-13324-CS302](#), and [AR-13324-CS304](#)), and reduces IOP potentially through several mechanisms: increasing trabecular outflow (Clinical Study Report [AR-13324-CS102](#); [Wang 2015](#)), decreasing aqueous humor production (Clinical Study Report [AR-13324-CS102](#); [Wang 2015](#)), and reducing episcleral venous pressure (Clinical Study Report [AR-13324-CS102](#); [Kiel 2015](#)). The ability to reduce aqueous production may be related to netarsudil *in vitro* inhibitory activity against monoamine transporters, including the norepinephrine transporter.

The present study is a Phase 2 efficacy and safety study comparing netarsudil ophthalmic solution 0.02% and 0.04% to its placebo administered QD over the course of 28 days. This study will run concurrently with a Phase 1 ocular and systemic safety study comparing netarsudil ophthalmic solution 0.02% and 0.04% to its placebo after a single dose and daily QD dosing over a 7-day period (Protocol [AR-13324-CS104](#)). Both studies will recruit subjects with Japanese ethnicity within the second generation in the US.

1.2 Findings from Non-clinical and Clinical Studies

Non-clinical

Proof of concept for netarsudil in lowering IOP was established in primary pharmacology studies in 2 species, rabbits and monkeys. Safety pharmacology (central nervous system, respiratory, and cardiovascular) of netarsudil was investigated in rats and dogs. Pharmacokinetics/bio distribution of netarsudil was assessed after systemic and ocular administration of netarsudil. Ocular toxicity was investigated in studies up to 6 months in rabbits and up to 9 months in monkeys. Repeated dose toxicity of systemically administered netarsudil was investigated in studies up to 28 days in rats and dogs. Reproductive toxicity was investigated in rats and rabbits. The non-clinical program for netarsudil also included a standard range of genotoxicity tests.

Clinical

The clinical development of netarsudil ophthalmic solution includes pharmacokinetics, tolerability, and dose-response investigations. The assessment of the ocular and systemic safety of netarsudil ophthalmic solution 0.02% in two Phase 1 clinical studies (Clinical Study Reports [AR-13324-CS101](#) and [AR-13324-CS102](#)) has been completed. Results from a previous Phase 2 study (Clinical Study Report [AR-13324-CS201](#)) investigating a range of netarsudil concentrations (0.01%, 0.02%, and 0.04%) were used to select the appropriate concentrations of netarsudil ophthalmic solution to be tested in the present study (0.02% and 0.04%). Three well-controlled Phase 3 clinical studies (Clinical Study Reports [AR-13324-CS301](#), [AR-13324-CS302](#), and [AR-13324-CS304](#)) evaluating the safety and efficacy netarsudil ophthalmic solution 0.02% have been completed.

Detailed information on nonclinical and clinical studies completed with netarsudil ophthalmic solution is provided in the [Investigator's Brochure](#).

1.3 Risks and Benefits to Human Subjects

As no other compounds of this class are approved, and only early stage clinical experience is available, the risks and benefits are not well understood at this time. Given the pharmacology of this class of agents and the results of previous Phase 1, Phase 2, and Phase 3 clinical studies by the Sponsor (Clinical Study Reports [AR-13324-CS101](#), [AR-13324-CS102](#), [AR-13324-CS201](#), [AR-13324-CS202](#), [AR-13324-CS301](#), and [AR-13324-CS302](#), and [AR-13324-CS304](#)), it is expected that transient hyperemia of the conjunctiva will be observed. The reader should refer to the Investigator's Brochure for more detailed information on potential risks due to use of netarsudil ophthalmic solution.

The major potential benefit from exposure to netarsudil ophthalmic solution is reduction in IOP in subjects with open angle glaucoma (OAG) or ocular hypertension (OHT). A long-term benefit of reduced IOP could be slowing of disease progression and preservation of vision in subjects when measured over periods of months to years

2. STUDY OBJECTIVES

2.1 Primary Objective(s)

In this Phase 2 study, the primary objectives are to evaluate:

[figure not shown]
- The ocular hypotensive efficacy of netarsudil ophthalmic solution relative to its placebo over a 28-day period
- The ocular and systemic safety of netarsudil ophthalmic solution relative to its placebo over a 28-day period

2.2 Secondary Objective(s)

None.

3. INVESTIGATIONAL PLAN

Figure 1 Study Design

3.1 Overall Study Design and Plan

This will be a 28-day, double-masked, randomized, multicenter, placebo-controlled, parallel-group efficacy and safety trial evaluating reduction of elevated IOP with netarsudil ophthalmic solution. The purpose of this study is to assess the efficacy and safety of netarsudil ophthalmic solution (0.02% and 0.04%) compared to its placebo in Japanese or Japanese-American subjects that are at least 18 years of age with OAG or OHT.

All investigational products will be dosed in both eyes (OU) QD in the evening (PM). Subjects eligible to be enrolled in this study will be those of Japanese ethnicity within the second generation, with a diagnosis of either OAG or OHT that are on treatment with a topical ocular hypotensive medication. Approximately 180 subjects will be enrolled. Subjects who agree to participate in this study and are enrolled in the study will attend a total of 6 study visits: a Screening Visit, Qualification Visit #1, Qualification Visit #2/Day 1 (baseline), Week 1 (Day 8), Week 2 (Day 15), and Week 4 (Day 29).

Subjects currently using ocular hypotensive medications will be required to washout of their pre-study ocular hypotensive medication for a prescribed period (i.e., 5 days to at least 4 weeks, depending on the medication) prior to attending Qualification Visit #1. Subjects

eligible to be enrolled in this study must meet all inclusion criteria and none of the exclusion criteria at each of the Screening Visit and Qualification Visits #1 and #2. Subjects will receive a baseline eye examination including IOP measurements at the Screening Visit and Qualification Visits #1 and #2 and, if deemed eligible, will be enrolled at Qualification Visit #2 and assigned to placebo or 1 of 2 investigational products in a 1:1:1 ratio according to a computer-generated randomization list. Randomization will take place using Interactive Web Response System (IWRS) methodology and will stratify subjects by site.

Randomized subjects will dose the assigned investigational product in both eyes QD in the evening (between 20:00 and 22:00 hours) beginning on Day 1 and up to and including the evening prior to the final visit at Visit 6 (Week 4). Procedures conducted at each of study Visits 4-6 will include safety measures and efficacy measurements, including IOP assessments. At Visits 4-6 (Weeks 1, 2, and 4, respectively), IOP will be assessed at 08:00, 10:00 and 16:00 hours. Following completion of the Visit 6 (Week 4) study visit procedures, subjects will exit the study. For subjects who discontinue early, every possible effort will be made to assure there is a final visit that includes all examinations listed for Visit 6.0 (Week 4) and dilated ophthalmoscopy.

3.2 Rationale for Study Design and Control Group

In order to further evaluate the hypotensive efficacy of netarsudil ophthalmic solution relative to its placebo in subjects with OAG or OHT and to generate additional safety data for netarsudil, a double-masked, parallel group, 3-arm active- and placebo-controlled study design was selected.

As the intended route of administration for netarsudil ophthalmic solution is topical ocular, this is the route to be used in this study. The dosage regimen selected for this study is based on a previously completed Phase 2 study ([AR-13324-CS202](#)) and 3 completed Phase 3 studies ([AR-13324-CS301](#), [AR-13324-CS302](#), and [AR-13324-CS304](#)).

Efficacy and safety results with netarsudil ophthalmic solution to date have been generated in a mostly non-Japanese population. In order to ensure that similar results are observed in Japanese subjects, this study is being conducted in subjects of Japanese ethnicity.

3.3 Expected Duration of Subject Participation

Each subject is planned to undergo a minimum washout period of their current ocular hypotensive medications (if needed), followed by approximately 28 days of treatment. Treatment duration with the investigational product (IP) for this study will start on the evening of Visit 3 (Qualification Visit #2; Day 1) and end on the evening before Visit 6 (Week 4/Day 28).

4. STUDY POPULATION SELECTION

4.1 Study Population

A total of approximately 180 Japanese/Japanese-American subjects will be enrolled in this study at approximately 35 investigational sites in the US comprising a total of 60 subjects per treatment arm for each of the 3 treatment arms. Subjects will be at least 18 years of age with diagnosed OAG or OHT, each of whom meets all inclusion criteria and none of the exclusion criteria.

Planned enrollment numbers are higher (180 total, 60 subjects per arm) than statistically required for demonstrating efficacy (approximately 49 intent-to-treat [ITT] subjects per arm for 90% power) to account for the potential for subjects who do not complete the entire dosing period, or who have disqualifications. Over-enrollment (beyond 180 subjects) is to be undertaken only after communication between the investigational site and the Sponsor representative.

4.2 Inclusion Criteria

Subjects have to meet all of the following criteria at screening and qualification visits to enter into the study:

1. Must be 18 years of age or older
2. Be of Japanese ethnicity within the second generation proven by birth certificate or family tree. Japanese generation is defined as follows: 1st generation is defined as born in Japan, immigrated to US; 2nd generation is defined as parents are 1st generation, however, the subject was born in US as an American citizen
3. Diagnosis of open-angle glaucoma (OAG) or ocular hypertension (OHT) in both eyes (OAG in one eye and OHT in the fellow eye is acceptable)
4. Medicated intraocular pressure (IOP) \geq 15 mmHg and $<$ 30 mmHg in both eyes at screening visit (this also applies to treatment naïve subjects)
5. For OAG eyes, unmedicated (post washout) IOP \geq 15 mmHg and $<$ 35 mmHg in the study eye at 2 qualification visits (08:00 hour), 2-7 days apart. At second qualification visit IOP \geq 15 mmHg and $<$ 35 mmHg at 10:00 and 16:00 hours (in the same eye).
[REDACTED]
6. For OHT eyes, unmedicated (post washout) IOP \geq 22 mmHg and $<$ 35 mmHg in the study eye at 2 qualification visits (08:00 hour), 2-7 days apart. At second qualification visit IOP \geq 22 mmHg and $<$ 35 mmHg at 10:00 and 16:00 hours (in the same eye).
[REDACTED]

7. Best corrected visual acuity + 1.0 logMAR or better by ETDRS in each eye (equivalent to 20/200 or better Snellen visual acuity in each eye)
8. Be able and willing to give signed informed consent and follow study instructions

4.3 Exclusion Criteria

Subjects meeting any of the following criteria during screening or qualification evaluations (e.g., at the time of randomization) will be excluded from entry into the study:

Ophthalmic:

1. Clinically significant ocular disease (e.g., corneal edema, uveitis, or severe keratoconjunctivitis sicca) which might interfere with interpretation of the study efficacy endpoints or with safety assessments, including subjects with glaucomatous damage so severe that washout of ocular hypotensive medications for up to 8 weeks is not judged safe as it would put the subject at risk for further vision loss
2. Pseudoexfoliation or pigment dispersion component glaucoma, history of angle closure glaucoma, or narrow angles (i.e., Shaffer Grade 2 or less). Note: Previous laser peripheral iridotomy is NOT acceptable
3. Intraocular pressure ≥ 35 mmHg (unmedicated) in either eye (individuals who are excluded for this criterion are not allowed to attempt requalification)
4. Ocular hyperemia score of moderate (+ 2) at Qualification Visit #2
5. Previous glaucoma intraocular surgery, including selective laser trabeculoplasty (SLT) or argon laser trabeculoplasty (ALT) in either eye
6. Refractive surgery in either eye (e.g., radial keratotomy, photorefractive keratectomy [PRK], laser-assisted in situ keratomileusis [LASIK], corneal cross-linking)
7. Ocular trauma within the 6 months prior to screening, or ocular surgery or non-refractive laser treatment within the 3 months prior to screening
8. Recent or current evidence of ocular infection or inflammation in either eye. Current evidence of clinically significant blepharitis, conjunctivitis, keratitis, or a history of herpes simplex or zoster keratitis in either eye at screening
9. Use of ocular medication in either eye of any kind within 30 days of screening and throughout the study, with the exception of a) ocular hypotensive medications (which must be washed out according to the provided schedule), b) lid scrubs (which may be used prior to, but not after, screening), c) lubricating drops for dry eye (which may be used throughout the study), or d) non-steroid allergy drops (note: must not contain a vasoconstrictor) as prescribed by the Investigator

10. Mean central corneal thickness using optical pachymetry greater than 620 μm in either eye at screening
11. Any abnormality preventing reliable applanation tonometry of either eye (e.g., keratoconus)
12. Known hypersensitivity to benzalkonium chloride or excipients of netarsudil ophthalmic solution

Systemic:

13. Clinically significant abnormalities in laboratory tests at screening
14. Clinically significant systemic disease which might interfere with the study
15. Participation in any investigational study within 30 days prior to screening
16. Systemic medication that could have a substantial effect on IOP within 30 days prior to screening, or anticipated during the study, including any corticosteroid-containing drug regardless of route of administration
17. Women of childbearing potential who are pregnant, nursing, planning a pregnancy, or not using a medically acceptable form of birth control. An adult woman is considered to be of childbearing potential unless she is 1 year post-menopausal or 3 months post-surgical sterilization. All females of childbearing potential must have a negative urine pregnancy test result at the screening examination and must not intend to become pregnant during the study

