6.5.3 Pregnancy Testing

A urine human chorionic gonadotropin (hCG) pregnancy test (only for females who are not diagnosed as postmenopausal or surgically sterile) will be used in this study and performed at the screening visit to immediately confirm non-pregnancy eligibility for females of child-bearing potential.

The Sponsor will provide urine pregnancy tests to the sites. Expiration dates on the pregnancy tests will be reviewed and confirmed by the site prior to use.

If a female becomes pregnant during the study, the Investigator should notify the Sponsor immediately after the pregnancy is confirmed and the subject will be exited from the study. The Investigator should follow the progress of the pregnancy until the fetus is carried to term.

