- Symptomatology: Individuals will be asked "How are you feeling?"
- Recording of any AEs
- Best Corrected Visual Acuity
- A non-dilated eye examination will be performed, including IOP measurements and biomicroscopy. IOP must be measured within 30 minutes of the nominal time (i.e., 07:30 to 08:30 hours)

Any new or worsening of symptoms beyond those collected at baseline are to be entered as AEs.

Subjects are allowed to leave the Investigator's office between assessments, and eat and drink without restrictions. However, subjects are not to consume alcohol or engage in strenuous exercise.

7.3.8 Visit 5.1 (Week 2 [Day 15], for IOP and safety measurements at 10:00 hours)

Subjects will be examined and each examination will include:

- Symptomatology: Individuals will be asked “How are you feeling?”
- Recording of any AEs
- A non-dilated eye examination will be performed, including IOP measurements and biomicroscopy. IOP must be measured within 30 minutes of the nominal time (i.e., 09:30 to 10:30 hours)

Subjects are allowed to leave the Investigator’s office between assessments, and eat and drink without restrictions. However, subjects are not to consume alcohol or engage in strenuous exercise.

7.3.9 Visit 5.2 (Week 2 [Day 15], for IOP and safety measurements at 16:00 hours)

Subjects will be examined and each examination will include:

- Symptomatology: Individuals will be asked “How are you feeling?”
- Recording of any AEs
- A non-dilated eye examination will be performed, including IOP measurements and biomicroscopy. IOP must be measured within 30 minutes of the nominal time (i.e., 15:30 to 16:30 hours)

Subjects will be:

- Instructed to continue to administer their masked medication at home between 20:00 - 22:00 hours (taking the daily evening dose on that day)
- Instructed to return to the office with their study medication on Week 4 (Day 29)

7.3.10 Visit 6.0 (Week 4 [Day 29], for IOP and safety measurements at 08:00 hours)

Subjects will return to the Investigator’s office. The subject will be questioned about any missed doses and any changes in their health or concomitant medication use. Subjects will be examined and each examination will include:

- Heart rate and blood pressure
- Symptomatology: Individuals will be asked “How are you feeling?”
- Recording of any AEs

- Urine pregnancy test (tests for applicable female subjects of child bearing potential may be performed at any time point throughout Visit 6)

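### Pregnancy is an exclusion up to randomization, but the only scheduled pre-dose test is at screening (at least 30 days earlier after a prostaglandin or beta-antagonist washout) and the next follows the last planned dose

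*Protocol*

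**What the plan says.** **When eligibility applies.** Protocol 3.1 requires enrolled subjects to meet "none of the exclusion criteria at each of the Screening Visit and Qualification Visits #1 and #2". The lead-in to 4.3 says that anyone who meets an exclusion criterion "during screening or qualification evaluations (e.g., at the time of randomization) will be excluded from entry into the study". Sections 7.2 and 7.3.1 to 7.3.3 have the criteria reviewed again at Visits 2, 3.0, 3.1 and 3.2.

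**What exclusion 17 covers.** It bars "Women of childbearing potential who are pregnant, nursing, planning a pregnancy, or not using a medically acceptable form of birth control". A separate sentence in the same criterion deals with the test: "All females of childbearing potential must have a negative urine pregnancy test result at the screening examination".

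**When the test is done.** Protocol 6.5.3 describes one urine test, "performed at the screening visit to immediately confirm non-pregnancy eligibility for females of child-bearing potential". Appendix 2 repeats this, and 7.1 lists the test at Visit 1. The procedure lists for Visits 2 to 5 contain none. Section 7.3.10 and Appendix 1 add a second test at Visit 6. SAP 2.2 and SAP Appendix 1 show the same two occasions.

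**When dosing happens.** By 3.1 and 3.3, dosing starts on the evening of Day 1 and ends on the evening before Visit 6.

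**The concern.** The eligibility statement at randomization includes that the woman is not pregnant. The only scheduled evidence for it is a result from Visit 1. Washout, the gap between the qualification visits and any requalification all fall between that result and the first dose. A pregnancy that begins in this interval and is not recognised can be randomized and dosed with the plan followed exactly. The next scheduled test comes when planned dosing is over.

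By the protocol's own terms this matters. Pregnancy is an exclusion, a confirmed pregnancy leads to exit from the study (6.5.3), and pregnancies are followed to outcome with several outcomes reported as serious adverse events (6.9.8). The stake is subject safety and the soundness of the eligibility record. No efficacy endpoint or analysis depends on it.

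**Working it through.** The documents state no screening-to-randomization interval, so there is no figure of theirs to reproduce. The interval follows from the stated windows.

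**Inputs**
- Minimum washout before Visit 2 (Protocol 5.7.1, Table 1; summarised in 3.1 as "5 days to at least 4 weeks, depending on the medication"): prostaglandins and beta-antagonists 28 days; adrenergic agonists 14 days; muscarinic agonists and carbonic anhydrase inhibitors 5 days.
- Longest washout without contacting the sponsor (5.7.1): 56 days. This is a trigger for contact, not a cap.
- Visit 2 to Visit 3 (7.2): 2 to 7 days.
- Requalification after failing Visit 2 (7.2) or Visit 3 (7.3.1): up to 7 days each.
- Visit 6 (Appendix 1): Day 29 ± 3, so 25 to 31 days after Day 1.
- Assumption: washout starts on the day of screening, when the test is done.

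**Formula.** Age of the negative result at first dose = washout + requalification at Visit 2 (0 to 7) + Visit 2 to Visit 3 (2 to 7) + requalification at Visit 3 (0 to 7).

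| Prior medication | Shortest (days) | Longest without requalification, 56-day washout | Longest path in the windows |
|---|---|---|---|
| Prostaglandin or beta-antagonist | 28 + 2 = 30 | 56 + 7 = 63 | 56 + 7 + 7 + 7 = 77 |
| Adrenergic agonist | 14 + 2 = 16 | 63 | 77 |
| Muscarinic agonist or carbonic anhydrase inhibitor | 5 + 2 = 7 | 63 | 77 |

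At exactly the minimum washout and without requalification, the 4-week classes give 30 to 28 + 7 = 35 days. With no washout, the shortest interval is 2 days.

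**Between the two scheduled tests, 4-week classes.** Shortest 30 + 25 = 55 days; longest 77 + 31 = 108 days.

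**Reading exclusion 17 beside its neighbours.** Exclusions 10 (corneal thickness) and 13 (laboratory abnormalities) limit the condition itself to screening. Exclusion 4 (hyperemia) ties its condition to Qualification Visit #2. In exclusion 17 only the test sentence is tied to screening; being pregnant carries no such limit, so the lead-in carries it forward to randomization. IOP, by contrast, is measured again at both qualification visits.

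**A smaller mismatch.** Section 6.5.3 and Appendix 2 mention the screening test only; 7.3.10 and Appendix 1 have screening and Visit 6.

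**The case against.** The strongest reply is that the plan is consistent about the test. Exclusion 17 names screening as its time, and every schedule in both documents agrees. The lead-in to 4.3 is general and does not say that each test must be repeated. The protocol verifies other criteria once: corneal thickness at screening, and gonioscopy up to 3 months before randomization (6.13). This stands in part. A reader might infer a flat contradiction, and the documents do not support that: the test sentence and the schedule match. What remains is that the condition applies later than the evidence for it. For gonioscopy the protocol says how old a result may be at randomization; for pregnancy it gives no such allowance.

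Safeguards also exist. Exclusion 17 requires acceptable contraception and no intent to become pregnant. The criteria are reviewed four more times before randomization, and changes in health are asked about at Visits 2, 3.0, 4.0 and 5.0. A reader might infer that nothing could detect a pregnancy before Visit 6. That goes too far, because a known or suspected one may surface at any of these points and, once confirmed, leads to exit. None of them is a test, so an unrecognised pregnancy is still missed.

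Materiality is uncertain. The number of women of childbearing potential is not given and may be small. Reproductive toxicity was studied (1.2), but its results are not in these documents. SAP 8.2 expects about 10 ITT subjects per arm after early closure. These points limit the practical effect in this study; they do not close the gap in the protocol.

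**Conclusion.** The point holds as a gap in verification that bears on subject safety. Pregnancy bars entry up to randomization, yet the only scheduled pre-dose test is at screening and the next follows the last planned dose. For women washing out a prostaglandin or beta-antagonist, the result is at least 30 days old at first dose and up to 77 days old within the stated windows. The two scheduled tests are then about 55 to 108 days apart.

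This rests on washout starting at screening. The 77 days need an 8-week washout, the widest visit gap and a full requalification week after both visits. It is the longest in-window path, not a typical one, and can be exceeded because 56 days is not a hard limit. A reader might infer that most washout subjects wait at least 30 days. The documents do not give the mix of prior medication classes (SAP 6.2 only plans to tabulate it), and across all washout classes the range starts at 7 days.

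**What to change.** The sponsor should reconcile exclusion 17 (in 4.3 and the synopsis), 6.5.3, 7.1, 7.3.1, Appendix 1, Appendix 2 and SAP Appendix 1 with the eligibility timing in 3.1 and the 4.3 lead-in. The aim is that the scheduled evidence of pregnancy status supports the eligibility statement made at randomization. Which testing rule applies is the sponsor's clinical decision.

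The same revision should align 6.5.3 and Appendix 2, which mention screening only, with 7.3.10 and Appendix 1, which have screening and Visit 6.

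The cost is wording in the protocol and in the SAP schedule. At most it also means using urine kits that the sponsor already supplies (6.5.3) at a visit that subjects already attend.
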